[figure not shown]

Association between Vitamin D and The Development of Uterine Fibroids

2018.3.15

Study objectives The primary objective of this part is to assess the efficacy of supplementation with vitamin D on inhibiting the development of uterine fibroids in one year and two years. The secondary objective of this study is to evaluate the safety of supplementation with vitamin D in subjects.

Trial design This is an open-label, randomised controlled trial. After signing of informed consent, patients with vitamin D deficiency ($12 \text{ ng/ml} \leq \text{Serum 25-hydroxyvitamin D}_3 < 20 \text{ ng/ml}$) and uterine fibroids will be randomly assigned in a 1:1 ratio to intervention group A or control group B. Intervention group A will accept an oral dose of 1600 IU/day vitamin D₃ for up to 2 years. Control group B will receive 2 years follow-up. Patients with vitamin D insufficiency ($20 \text{ ng/ml} \leq \text{Serum 25-hydroxyvitamin D}_3 < 30 \text{ ng/ml}$) and uterine fibroids will be randomly assigned in a 1:1 ratio to intervention group C or control group D. Intervention group C will accept an oral dose of 800 IU/day vitamin D₃ for up to 2 years. Control group D will receive 2 years follow-up. Gynecologic ultrasound examinations will be performed every three months. The mount, location and size of the uterine fibroids will be documented (the transverse, longitudinal, and antero-posterior diameters of fibroids will be documented at each efficacy ultrasound examination for volume calculation). Percent change in volume of the total fibroids compared to baseline in different groups (baseline = last value obtained before randomization). Three perpendicular diameters (d₁, d₂, and d₃) were collected for each fibroid, and the volume of each fibroid (in cm³) was calculated with the ellipsoid formula: $4/3 * \pi * (d_1 * d_2 * d_3)/8$. For each patient, the total volume of fibroids (defined as the sum of the volumes of all the fibroids detected) was also calculated. The safety of vitamin D in subjects with uterine fibroids will be evaluated, including blood routine examination, electrolyte, hepatic and renal function, liver and urinary system ultrasound, and serum 25-hydroxyvitamin D₃. Vitamin D₃ Drops are purchased from Sinopharm star shark pharmaceutical (xiamen) co., LTD. An overview of the study design is shown in Figure 2 and Table 2.

[figure not shown]

Figure 2 flow diagram.

Table 2:time of date collection

Follow-up	1	2	3	4	5	6	7	8	9

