Months	0	3	6	9	12	15	18	21	24
The form of follow-up	Out-patient								
Informed consent	X								
Medical history	X								
Physical examination	X								
Serum 25-hydroxyvitamin D ₃	X	X	X	X	X	X	X	X	X
Urine pregnancy test	X	X	X	X	X	X	X	X	X
Gynecologic ultrasound	X	X	X	X	X	X	X	X	X
Hepatic and renal function	X		X		X		X		X
Electrolyte	X		X		X		X		X
Blood routine examination	X		X		X		X		X
Liver and urinary		X			X				X
System ultrasound			X						
Side-effect assessment		X	X	X	X	X	X	X	X
Changes in menstruation		X	X	X	X	X	X	X	X
Adverse event assessment		X	X	X	X	X	X	X	X
Vitamin D receptor genotype	X								

Sample size According to a previous study, the volume of uterine fibroids was 8.2 (2.1-30.5) cm³ after the supplement of vitamin D 12 months and 11.4 (5.5-22.3) cm³ in the control group, respectively. On the basis of a 0.9 power to detect a significant difference ($\alpha=0.05$, one-sided), 320 participants will be required for the four groups and in a 1:1:1:1 ratio. Allowing for a 10% withdrawal rate, we plan to include 360 patients in the whole trial.

Inclusion criteria

1. Patients are willing to cooperate with the follow-up and sign informed consent;
2. Females aged 35-50 who are diagnosed as having uterine fibroids by transvaginal or abdominal ultrasonography;
3. The maximum average diameter of intramural myoma is $\leq 4\text{cm}$, $\geq 1\text{cm}$; The amount of myoma is less than 4;
4. Serum 25-hydroxyvitamin D₃ $< 30\text{ ng/ml}$, $\geq 12\text{ ng/ml}$.

Exclusion criteria

1. Patients with heavy menstrual bleeding ($>80.0\text{ mL}$), menstrual disorders, pelvic discomfort, infertility, or other indications for operation;

2. Patients complicated with myoma degeneration and adenomyosis that were suspected or diagnosed by ultrasound or gynecologic examination;
3. Allergic to vitamin D₃;
4. Use of sexual hormone, mifepristone, gonadotropin-releasing hormone agonist (GnRHa), or other medication which is likely to interfere with uterine fibroids within 3 months;
5. Pregnancy, lactation, postmenopause, or planned pregnancy within two years;
6. Suspected or identified as other tumors of genital tract;
7. History of osteoporosis or vitamin D deficiency taking vitamin D supplements within previous one month;
8. History of autoimmune diseases, infectious diseases (tuberculosis, AIDS), autoimmune diseases, digestive system diseases (malabsorption, crohn disease, and dysentery);

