9. Alanine aminotransferase (ALT) or aspartate transaminase (AST) more than 3 times of the normal upper limit, total bilirubin (TBIL) more than 2 times of the normal upper limit;
10. Creatinine levels ≥ 1.4 mg/dL (123 μ mol/L) or creatinine clearance ≤ 50 mL/min;
11. History of malignant tumors;
12. Simultaneous participation in another clinical study with investigational medicinal product(s) or researcher thinks the subjects are not suitable for this trial.

Outcomes measures Primary outcomes: percent change in volume of the largest fibroid and total fibroids compared to baseline (baseline = last value obtained before randomization; measured by ultrasound examination). Secondary outcomes: percentage of subjects undergoing other medical or surgical treatment, hypercalcemia, urinary calculus, abnormal liver and renal function. Ultrasound examinations will be performed by a physician well experienced in gynecology. If possible, the same examiner should conduct all examinations of a subject throughout the study and the same ultrasound machine (per site) should be used throughout the study. For each subject, the most appropriate ultrasound method (transvaginal or abdominal) should be used depending on fibroids location and this method should be used consistently throughout the study.

Withdrawal Subjects must be withdrawn from the study when one of the following criteria occurs:

1. At their own request. At any time during the study and without giving reasons, a subject may decline to participate further. The subject will not suffer any disadvantages as a result;
2. In the investigator's opinion, continuation of the study treatment would be harmful to the subject's health;
3. Obvious non-compliance;
4. Lost to follow-up;
5. Pregnancy;
6. Other medical or surgical treatments of uterine fibroids.
7. Receive other medical treatments which may affect the level of serum 25-hydroxyvitamin D₃ or other surgical treatments.

8. The level of serum calcium > 3.5 mmol/L or serum 25-hydroxyvitamin D₃ > 100 ng/mL.

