Safety assessments Safety will be assessed by renal and liver function test, electrolyte, routine blood test, and serum 25-hydroxyvitamin D₃. Urine pregnancy test and serum 25-hydroxyvitamin D₃ level will be detected every three months. Other indicators are detected during the period of screening and after the treatment of every six months. Liver and urinary system ultrasound will be conducted after the treatment of 12 months and 24 months. The occurrence of any adverse events in trial participants will be recorded in the case report forms during each patient visit. We will withdraw patients who have severe adverse events, as it is unsafe for them to continue the trial. Meanwhile, we will give them relevant medical care and follow them up until the reaction has terminated.

Statistical analysis Statistical analyses will be performed using SPSS version 22.0 for Windows (SPSS Inc., Chicago, IL, USA). The randomisation sequence is generated by the use of the SPSS software. The normality of distribution of continuous variables are tested by one-sample Kolmogorov-Smirnov test. Continuous variables with normal distribution are reported as mean (standard deviation); non-normal variables are presented as median (interquartile range). Means of 2 and 3 or more continuous normally distributed variables, respectively, are compared by independent samples Student's t test or one-way ANOVA test. Mann-Whitney U test and Kruskal-Wallis test are used, respectively, to compare means of 2 and 3 or more groups of variables not normally distributed. The frequencies of categorical variables are compared using Pearson χ^2 or Fisher's exact test, when appropriate. A value of $P < 0.05$ is considered significant.

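### Both primary outcomes rest on ultrasound diameters in an open-label trial with follow-up-only controls, and the plan does not say that the examiner is masked to arm

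*Combined protocol and SAP*

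**What the plan says.** Trial design states: "This is an open-label, randomised controlled trial". Groups A and C take vitamin D₃ drops. For the comparators it says "Control group B will receive 2 years follow-up" and "Control group D will receive 2 years follow-up", and no placebo is mentioned.

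Outcomes measures gives two primary outcomes: "Primary outcomes: percent change in volume of the largest fibroid and total fibroids compared to baseline". Trial design sets the calculation: three perpendicular diameters per fibroid go into the ellipsoid formula, and baseline is the last pre-randomisation value.

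On who measures, Outcomes measures says: "Ultrasound examinations will be performed by a physician well experienced in gynecology". It adds: "If possible, the same examiner should conduct all examinations of a subject throughout the study". It also asks for one machine per site and one ultrasound route per subject.

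Table 2 puts serum 25-hydroxyvitamin D₃ and the gynecologic ultrasound at the same nine visits, months 0 to 24. Safety assessments confirms that the serum "level will be detected every three months". The document does not say who sees those results. It contains no statement on masking the examiner, on blinded or independent reading of images, or on withholding earlier measurements. Figure 2, the flow diagram, is not reproduced in the available text.

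**The concern.** An open-label design settles what patients and prescribers know. It does not settle what the person placing the calipers knows, and masked measurement is compatible with it. Caliper placement involves judgement, and the ellipsoid formula multiplies three readings, so small shifts in diameter become larger shifts in volume.

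The rules in Outcomes measures are useful. They reduce noise, and an examiner who always reads slightly low does so at baseline too, so most of that offset cancels in percent change. They do not deal with a shift that starts after randomisation and depends on arm. Baseline precedes allocation, so such a shift would appear only in the follow-up value and would not cancel. An examiner who follows the same woman throughout may also remember her group. If the three-monthly 25-hydroxyvitamin D results reach the examiner, they could reveal the arm as well.

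If examiners know the arm, expectation could enter both primary outcomes at each of the eight post-baseline scans. The planned t test or Mann-Whitney test cannot separate that from a treatment effect.

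**Working it through.** The plan states no measurement error, no SD for percent change and no target difference in percent change, so there is no figure of its own to reproduce. What follows is a sensitivity calculation.

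**Inputs from the documents.** 12-month volumes of 8.2 and 11.4 cm³ in the previous study, and 320 participants in four equal groups (Sample size); eligible fibroid diameter 1 to 4 cm (Inclusion criteria); the ellipsoid formula (Trial design).

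**Assumed inputs.** A shift e of 0.5 or 1 mm; the number of diameters shifted, k; the share of treated patients affected, f; the SD of the log volume ratio, 0.4 to 0.8.

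**Yardstick.** 1 − 8.2/11.4 = 28.1%. This compares group volumes at 12 months, not percent change from baseline, so it only sets a scale.

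**Sphere-equivalent diameter.** d = (6V/π)^(1/3): 11.4 cm³ gives 2.79 cm and 8.2 cm³ gives 2.50 cm.

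**Constant offset.** With 1 mm under-reading at both baseline and follow-up, ((2.50 − 0.1)/(2.79 − 0.1))³ − 1 = −29.0%, against a true −28.1%. A fibroid that does not change still reads 0%. A constant offset hardly matters.

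**Shift after randomisation in one arm.** Apparent volume reduction = 1 − (1 − e/d)^k. With e = 1 mm and k = 3:

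| Diameter | Volume reduction | Share of 28.1% |
|---|---|---|
| 1 cm | 27.1% | 97% |
| 2 cm | 14.3% | 51% |
| 2.79 cm | 10.4% | 37% |
| 3.5 cm | 8.3% | 30% |
| 4 cm | 7.3% | 26% |

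The share falls below one third above 3.1 cm. At 2.79 cm it is 25% if two diameters shift, 13% if one shifts, and 19% for 0.5 mm on all three.

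**Chance of a false benefit.** Take n = 320/4 = 80 per arm, no true effect and a two-sided 0.05 test, so the nominal rate in the favourable direction is 2.5%. The rate is 1 − Φ(1.96 − f·|k·ln(1 − e/d)|/SD × √(n/2)). For d = 2.5 cm, k = 3, f = 1 and e = 1 mm, |3·ln(0.96)| = 0.1225. With SD 0.4, 0.1225/0.4 × √40 = 1.94, giving 49.1%.

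| Scenario | 0.5 mm, SD 0.4 / 0.6 / 0.8 | 1 mm, SD 0.4 / 0.6 / 0.8 |
|---|---|---|
| 2.5 cm, three diameters, all treated | 15.8 / 9.3 / 6.9% | 49.1 / 25.2 / 16.1% |
| 2.5 cm, three diameters, half of treated | 6.9 / 5.0 / 4.3% | 16.1 / 9.4 / 7.0% |
| 2.5 cm, one diameter, all treated | 5.0 / 4.0 / 3.6% | 9.4 / 6.3 / 5.1% |
| 4 cm, three diameters, all treated | 8.6 / 5.9 / 4.8% | 22.4 / 12.3 / 8.7% |

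A simulation of the first row with the Mann-Whitney test on percent change (6000 runs) gave 14.3 / 8.8 / 7.0% and 47.8 / 23.7 / 16.0%, in line with the formula.

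**The case against.** The strongest reply is that this is an absence, not an admitted defect. No passage says examiners know the arm or receive the 25-hydroxyvitamin D results. That is right, and it is why the wording here is that masking is not specified.

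The second reply is that the false-benefit rates stack assumption on assumption and run from about 4% to 49%. The top end sits poorly with the plan's own sizing. If the target were the 28.1% contrast (log ratio 0.329), 80 per arm at one-sided 0.05 and 90% power would imply an SD of 0.329 × √40/(1.645 + 1.282) ≈ 0.71. At that SD the first table row becomes about 8% for 0.5 mm and 19% for 1 mm. At 2.79 cm instead of 2.5 cm, the 49% becomes 41%. These points stand as limits on the upper figures, although the 0.71 is itself inferred. The two-sided test works the other way: at the one-sided 0.05 used in Sample size, the first row becomes 12 to 25% and 25 to 62%, against a nominal 5%. Total volume in women with two or three fibroids was not modelled.

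The third reply concerns the remedy. Where one physician both prescribes and measures, masking is not achievable without a second person. An examiner who took the earlier readings may also recall them. Both limits are real and are carried into the recommendation. Neither is a reason to leave masking unstated where it can be done.

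**Conclusion.** The concern holds. The open-label design, the follow-up-only controls, the dependence of both primary outcomes on operator-placed diameters and the absence of any masking statement can all be read directly from the text. Following the measurement procedure as written would allow an arm-dependent shift after randomisation that the analysis cannot detect or remove.

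Whether such a shift would occur, and how large it would be, is unknown. Under the assumed 1 mm on all three diameters, it would amount to between about a quarter and nearly all of the planning contrast across the eligible size range. Smaller or partial shifts give less. The false-benefit figures are uniform-bias scenarios, not expected rates, and the case for masking does not depend on any one of them. This is a recommended change, held with medium confidence because the harm depends on examiners knowing the arm.

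**What to change.** Add to Outcomes measures that the existing examiners are masked to arm, by these steps:

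- Ultrasound requests carry the study number only.
- Arm and on-study 25-hydroxyvitamin D results are withheld from the examiner until the current diameters are entered.
- Earlier measurements are withheld, and a map of fibroid locations is supplied so that lesions can be matched.
- Participants are asked not to mention supplements to the examiner.
- Where existing staffing allows, the prescriber does not measure that patient's fibroids. Where it does not, the protocol should say so, because masking to arm cannot be claimed there.

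If examiners are already masked, one sentence recording it would close most of the gap.

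The cost is a few sentences and a changed request form, with no extra scans. The downsides are some accidental unmasking, slightly harder matching in women with two or three fibroids, and minor scheduling effort. A second physician may be needed where one now does both jobs. The documents give no site staffing, so that part remains conditional.

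### Mandatory withdrawal from the study, rather than from treatment alone, loses fibroid volumes after randomisation, and the visible text gives these patients no later scan and no analysis set

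*Combined protocol and SAP*

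**What the plan says.** The Withdrawal section opens with "Subjects must be withdrawn from the study when one of the following criteria occurs" and lists eight criteria. It has no category for stopping vitamin D while staying in follow-up. Five of the criteria matter here:

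- Criterion 2: in the investigator's opinion, "continuation of the study treatment would be harmful". Under Trial design only groups A and C receive a study treatment; B and D are followed up.
- Criterion 3: "Obvious non-compliance", not defined. The control groups have no product to comply with.
- Criterion 6: "Other medical or surgical treatments of uterine fibroids". Outcomes measures also lists the "percentage of subjects undergoing other medical or surgical treatment" as a secondary outcome.
- Criterion 7: "Receive other medical treatments which may affect the level of serum 25-hydroxyvitamin" D₃, with a second limb covering other surgery.
- Criterion 8: "The level of serum calcium > 3.5 mmol/L or serum 25-hydroxyvitamin" D₃ above a stated limit.

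Safety assessments adds: "We will withdraw patients who have severe adverse events, as it is unsafe for them to continue the trial". The only follow-up it describes for these patients lasts until the reaction is over.

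Table 2 schedules gynaecologic ultrasound at months 0 to 24 every three months and does not say what happens to the schedule after withdrawal. The Statistical analysis section lists tests that compare groups, with P < 0.05. It names no analysis set and no rule for missing volumes. The only visible provision for withdrawal is the 10% allowance under Sample size. Figure 2, the flow diagram, was not available for this review, so a statement there cannot be excluded.

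**The concern.** The primary outcomes are percent changes in fibroid volume, and the objective names both one year and two years. A patient who leaves the study has no later volume. Some reasons for leaving exist only, or more plausibly, in the vitamin D groups, and one reason (fibroid treatment) can follow from growth itself. The patients with a month-24 volume may therefore no longer be the groups that randomisation created. Month 12 is less exposed, because anyone who leaves after month 12 still has that volume.

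Two kinds of loss need separating. After criteria 2, 3 and 8, and the part of criterion 7 about treatments affecting 25-hydroxyvitamin D, a later volume would still be informative, and a scan not done cannot be recovered by any analysis. After fibroid treatment, pregnancy, or surgery on the uterus or fibroids, a later scan would not help. What is missing there is a rule for the volumes already collected. Own request and loss to follow-up are largely unavoidable and are not the point.

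**Working it through.** **The plan's own figure.** Inputs from Sample size: 320 required, 10% withdrawal, 360 planned. 320 / 0.9 = 355.6, so 356, and 360 × 0.9 = 324, which is at least 320. The inflation reproduces, but it protects only the count of patients.

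**Set-up for the illustrations.** From the documents: 8.2 and 11.4 cm³, and 360 / 4 = 90 per group. Assumed: log growth is normal with SD 0.6 (range 0.4-0.8). A patient leaves when a latent score exceeds z(1-p), where p is the leaving rate and r the correlation of the score with growth. Earlier volumes are not used. The documents give no leaving rate by arm and no value of r.

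**A. No true effect, unequal leaving.** The mean growth of those who stay is shifted by -SD × r × φ(z(1-p))/(1-p).

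Worked case, 5% control and 15% treated, r = 0.5:
- Control: -0.6 × 0.5 × 0.1031/0.95 = -0.0326.
- Treated: -0.6 × 0.5 × 0.2332/0.85 = -0.0823.
- False difference: -0.0497 (simulated -0.0489).
- Standard error: 0.6 × √(1/85.5 + 1/76.5) = 0.0944.
- One-sided error: Φ(-1.645 + 0.0497/0.0944) = Φ(-1.119) = 0.13 (simulated 0.134).

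One-sided error in favour of vitamin D, 20,000 simulated pooled t tests per cell:

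| Leaving, control vs treated | r = 0 | r = 0.3 | r = 0.5 | r = 0.7 |
|---|---|---|---|---|
| 10% vs 10% | about 0.05 | about 0.05 | about 0.05 | about 0.05 |
| 8% vs 12% | about 0.05 | 0.064 | 0.076 | 0.090 |
| 5% vs 15% | 0.051 | 0.088 | 0.134 | 0.197 |
| 12% vs 8% | about 0.05 | 0.039 | 0.032 | 0.025 |

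Two-sided error at r = 0.3/0.5/0.7 is 0.052/0.057/0.060 for 8% vs 12% and 0.057/0.080/0.123 for 5% vs 15%. Both versions are shown because the sample size is one-sided while Statistical analysis does not say which P < 0.05 is. SD cancels from these error rates. A separate run with the Mann-Whitney test at 5% vs 15% and r = 0.5 also gave about 0.13 one-sided.

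The r = 0 column shows that imbalance alone does nothing. In a mixed case, 5% leaves each arm for growth-related reasons (r = 0.5 or 0.7) and about 10% more treated patients leave for unrelated reasons. Error stays at 0.048-0.051.

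**B. True effect present, leaving for fibroid treatment.** Shift in the treated arm: ln(8.2/11.4) = -0.329. The same growth threshold applies in both arms, so fewer treated patients cross it. With a = z(1-p) - r × shift/SD, the treated mean among those who stay is shift - SD × r × φ(a)/Φ(a).

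Worked case, 5% of controls leaving, r = 0.5:
- a = 1.645 + 0.5 × 0.329/0.6 = 1.919.
- Treated: -0.3295 - 0.3 × 0.0651 = -0.3490.
- Control: -0.3 × 0.1086 = -0.0326.
- Difference: -0.3164, so 0.0131/0.3295 = 4.0% of the effect is lost.

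| Controls leaving | r = 0.3 | r = 0.5 | r = 0.7 |
|---|---|---|---|
| 2% | 0.8% | 2.1% | 3.7% |
| 5% | 1.5% | 4.0% | 7.2% |
| 10% | 2.4% | 6.2% | 11.5% |

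Over SD 0.4-0.8 the whole range is about 0.8-12%. The effect is understated, not exaggerated.

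**The case against.** The strongest case against is that the reasons likely to differ by arm and the reason likely to track growth are not the same reasons. Harm, non-compliance, other treatments and laboratory limits may fall mainly on the vitamin D groups, but nothing in the documents says why they would pick out fast-growing fibroids. Fibroid treatment does track growth, but if vitamin D works it falls mainly on controls, and that bias is conservative. This objection stands. A reader might infer that unequal withdrawal by itself inflates the false-positive rate, or that the plan favours vitamin D. The r = 0 column and the 12% vs 8% row show that neither follows.

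A reader might also infer that the sponsor will discard earlier volumes or analyse completers only. The documents do not say so; they do not say how those volumes will be used.

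Other limits also stand. Indications for operation are excluded at entry, so low rates of fibroid treatment are plausible. The 8.2 and 11.4 figures are volumes at 12 months, used here as a contrast in log growth. The primary outcome is percent change. A rank test may be used if the data are not normal.

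What the objection does not remove is the rule itself. Withdrawal from the study is mandatory, and no visible text continues the scans. Without them the sponsor could not show which of these cases had occurred.

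**Conclusion.** The point holds as a cheap improvement, not as a demonstrated bias. Followed as written, the Withdrawal section loses outcome volumes after randomisation, chiefly at month 24, and the visible text has no analysis set for deciding who is compared.

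The size and direction of any bias are unknown. With leaving unrelated to growth, one-sided error is about 0.05 even at 5% vs 15%. It rises only if fast growers leave the vitamin D arm more often than control: to about 0.06-0.09 at 8% vs 12%, and about 0.09-0.20 at 5% vs 15%, a strong assumption. All of this rests on assumed correlations of 0.3-0.7. Control patients leaving for fibroid treatment would cost about 1-12% of the effect under assumed rates of 2-10%, in the conservative direction. The absence of a follow-up or analysis-set statement is established for the visible text only.

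**What to change.** Leave the treatment-stopping criteria unchanged, and separate stopping treatment from leaving the study.

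- **Criteria 2, 3 and 8, and the part of criterion 7 on treatments affecting 25-hydroxyvitamin D:** continue the ultrasounds already scheduled to month 24 unless consent is withdrawn or the patient cannot be reached. Record reason and date of stopping by arm.
- **Analysis set:** make the primary analysis all randomised patients in their assigned arm, whatever their compliance. Define non-compliance and keep the compliant subset secondary.
- **Fibroid treatment, pregnancy, and surgery affecting the uterus or fibroids:** keep the quarterly volumes up to the event under a prespecified rule. A repeated-measures model is one option among several; it relies on leaving being explained by volumes already measured. Still count fibroid treatment as a secondary outcome.
- **Severe adverse events:** Safety assessments says it is unsafe for these patients to continue the trial. Reconcile that statement with the Withdrawal section and state whether any outcome measurement follows. The clinical decision is the sponsor's.

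Cost: protocol and analysis wording, plus scans already in Table 2. If all 36 expected leavers (10% of 360) left for the reasons in the first bullet, at month 12 on average, 36 × 4 = 144 scans would be kept, about 4% of the 360 × 9 = 3,240 scheduled. Fewer are kept if some leave for other reasons, more if leaving is earlier. The downside is that the effect is estimated under actual adherence and may be slightly diluted.

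### A Kolmogorov-Smirnov pre-test of unstated form chooses between t test and Mann-Whitney for the primary percent-change outcomes, so the primary analysis has no fixed effect measure.

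*Combined protocol and SAP*

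**What the plan says.** The Outcomes measures section defines the primary outcomes as "percent change in volume of the largest fibroid and total fibroids compared to baseline". The Study objectives section sets the aim as "inhibiting the development of uterine fibroids in one year and two years". Under Trial design there are two separately randomised strata: deficient patients "will be randomly assigned in a 1:1 ratio to intervention group A or control group B", and insufficient patients "will be randomly assigned in a 1:1 ratio to intervention group C or control group D".

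No test is named for these outcomes. The Statistical analysis section has one rule for all continuous variables. It starts with "The normality of distribution of continuous variables are tested by one-sample Kolmogorov-Smirnov test". Variables found normal "are compared by independent samples Student's t test or one-way ANOVA test". For the rest, "Mann-Whitney U test and Kruskal-Wallis test are used, respectively, to compare means of 2 and 3 or more groups of variables not normally distributed".

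The section gives no level for the normality test and no correction for a mean and SD estimated from the same data. It does not say whether normality is tested by arm, by pooled data, by visit or once per variable. It does not say that one choice applies to all primary comparisons.

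**The concern.** A t test on percent change targets a difference in arithmetic means. Mann-Whitney targets a shift in ranks; it does not compare means, although the plan describes it so. Letting trial data choose between them means that the primary question is settled only after outcomes are seen, in an open-label trial. Two volumes, two strata and two time points give up to 2 × 2 × 2 = 8 primary comparisons. If some are reported as mean differences and others as rank tests, results cannot be set side by side across strata or years.

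Percent change has a floor at −100% and no ceiling, so some right skew is plausible. Whether the pre-test would flag it depends on the form of the test and on a spread that the plan does not give.

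**Working it through.** **The plan's own figures.** The plan gives no operating characteristics for this rule. The figure used here is n per arm: 320 evaluable / 4 groups = 80 (Sample size section). The 320 itself could not be reproduced from the planning volumes. For example, on the log scale, one-sided, with SDs taken from the ranges read as quartiles, n per group = (1.645 + 1.282)² × (1.98² + 1.04²) / ln(11.4/8.2)² ≈ 396. That is a separate matter; here 80 only sets the sample size.

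**Assumptions.** Percent change = 100 × (R − 1), where R is the follow-up/baseline volume ratio and ln R is normal with SD s. The documents give no s, so it ranges from 0.2 to 0.8 (skewness of percent change about 0.6 to 3.7). Each arm is tested at 5%; ranks are used if either arm fails; each comparison makes its own choice; both strata have the same distribution. Results come from 5,000 to 6,000 simulated trials per setting.

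**Two forms of the pre-test, n = 80.**
- Uncorrected (parameters treated as known): critical D = 1.358/√80 = 0.152. Its true size on normal data is about 0.005%, not 5%.
- Corrected for estimated mean and SD (Lilliefors): critical D = 0.099 by simulation.

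**Chance of mixed tests.** If one arm is flagged with probability q, a comparison goes to ranks with probability p = 1 − (1 − q)², and the two strata differ with probability 2p(1 − p). The maximum is 50%, at p = 0.5. Example: uncorrected, s = 0.5, q = 0.252, so p = 1 − 0.748² = 0.44 and 2 × 0.44 × 0.56 = 49%, against 50% simulated.

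**True effect for power.** The standardised effect for which 80 per arm gives the stated 90% one-sided power is (1.645 + 1.282) × √(2/80) = 0.463 SD of ln R. Power below is two-sided at 5%.

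| s | Arm flagged, uncorr. / corr. | Strata get different tests, uncorr. / corr. | t and Mann-Whitney disagree on significance (true effect) | Power, two-stage rule, uncorr. / corr. | Power, t on log ratio |
|---|---|---|---|---|---|
| 0.2 | 0.5% / 27% | 2% / 49% | 6% | 82.6% / 82.3% | 82.8% |
| 0.3 | 3% / 49% | 11% / 39% | 7% | 81.1% / 80.8% | 82.9% |
| 0.4 | 11% / 75% | 31% / 13% | 8% | 81.7% / 82.7% | 83.8% |
| 0.5 | 25% / 89% | 50% / 2% | 10% | 80.2% / 81.0% | 82.6% |
| 0.6 | 47% / 97% | 41% / 0.1% | 12% | 81.0% / 81.1% | 82.9% |
| 0.7 | 68% / 99% | 18% / 0% | 15% | 81.6% / 81.6% | 83.7% |
| 0.8 | 85% / 99.8% | 4% / 0% | 17–18% | 80.7% / 80.7% | 82.7% |

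With no true effect, the two-stage rule rejects in 4.6 to 5.7% of trials over this range, under either form.

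**The case against.** Several stronger readings are tempting, and the documents do not support them.

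- *The pre-test barely detects skew.* A reader might infer this from the known leniency of the uncorrected test. It holds only for that form and for s of about 0.4 or less. From s = 0.5 the corrected form flags at least 89% of arms. The plan states neither the form nor the spread. Nor does weak detection cause mixing: a test that almost never rejects would almost always choose the t test (2% mixed at s = 0.2, uncorrected). Mixing peaks at intermediate detection.
- *The planning volumes prove the skew.* The 8.2 (2.1-30.5) and 11.4 (5.5-22.3) cm³ are follow-up volumes between patients. Percent change divides out baseline, and entry criteria limit fibroid size and number. If the log SDs implied by these ranges, ln(30.5/2.1)/1.349 = 1.98 and ln(22.3/5.5)/1.349 = 1.04, did apply to the ratio, practically every comparison would go to ranks and there would be no mixing.
- *The test is chosen afresh eight times.* The plan classifies variables and does not state the unit. One choice per variable, shared by both strata, is an equally natural reading. The mixing percentages apply only to the separate-choice reading.
- *False positives or a serious power loss.* Type I error is near nominal. The rule has about the same power as always using Mann-Whitney, and the gain from the log-ratio test is measured under lognormal data, which favour that test.
- *The pre-test is why no interval is reported.* The plan names no confidence interval on the t-test branch either.

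What remains is that the plan states a data-driven rule, fixes no single effect measure for the primary outcomes, and does not rule out mixed tests.

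**Conclusion.** The point holds as one of definition and comparability, not of error control. That the choice is data-driven, and that the form, level and unit of the pre-test are unstated, follows from the text alone. The size is conditional on 80 per arm, lognormal ratios with s between 0.2 and 0.8, and a separate choice per comparison. Different tests in the two strata would then occur in about 2 to 50% of trials with the uncorrected pre-test (peak near s = 0.5) and about 0 to 50% with the corrected one (peak near s = 0.2). The choice can matter for the conclusion, since the two tests disagree on significance in about 6 to 18% of trials with a true effect. The two-sided power cost against a log-ratio t test is about 1 to 3 points from s = 0.3 upward and under 1 point at s = 0.2. This is a cheap improvement rather than a flaw that threatens the trial.

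**What to change.** Remove the normality pre-test as the rule for the primary outcomes. State one analysis for both volumes, both strata and both time points: ln(follow-up volume / baseline volume), compared A vs B and C vs D, with the difference back-transformed to a ratio or percent change and given with a 95% CI. State in advance the floor used for a volume of zero when fibroids are no longer detected. Keep Mann-Whitney as a sensitivity analysis. It gives the same result on percent change as on the log ratio, because one is a monotone function of the other (before any floor is applied), and it needs no floor.

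The cost is SAP wording only. There are two downsides. The target becomes the geometric rather than the arithmetic mean change, and the floor must be chosen before follow-up volumes are analysed. Fixing Mann-Whitney alone would also end the mixing, but would not by itself supply an effect estimate on the percent-change scale.
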